#### Use of Data for Power Calculation for Planned Main Trial

The proposed R34 is expected to provide information needed to power the planned, future RCT. The R34 is designed to provide adequate precision of estimates of the primary outcome(s) of the full trial. We will look at baseline measures of multiple outcomes, and how these change over time. We will examine correlations of outcomes within store over time, between participants (customers) within stores, and within participants over time. We will use these data to assess clustering, permitting us to estimate the ICC, and precision around it, and to modify our main trial sample size estimates as needed. Ultimately, this will address gaps in the research for others who want to perform interventions with similar outcomes.

#### **Power Calculation and Study Design**

This is a randomized group-treatment trial, where individual stores will be randomized to two study conditions: 1) usage of a web-based app (BUD) to order healthier food and beverages + in-store point-of-purchase promotional materials + limited subsidies (treatment); or 2) only in-store point-of-purchase promotional materials (comparison). In order to ensure a balanced study design, prior to randomization, we will stratify corner stores by two factors to balance potential confounders: 1) length of time in business at this location (>2 years vs <2 years); and 2) store size (0-2 aisles vs 2-4 aisles), and then randomize matched pairs to treatment versus comparison.

We recognize that clustering may occur, given that storeowners will share a change agent (BUD app) with other storeowners assigned to intervention group, and will potentially interact with each other as part of the functioning of the BUD app. We will control for baseline covariates of all participating stores that may predict study outcomes.

The feasibility pilot study is powered based on seeing impact at the corner store level. Store eligibility criteria for participation in the trial are as follows: 1) store owner/manager willing to order food through a smartphone or other internet-enabled device; 2) store located in a low-income neighborhood classified as a healthy food priority area in East Baltimore; 3) classified as small food store (< 4 aisles, < 2 cashier); 4) English, Korean, Spanish or Mandarin-speaking; and 5) located >0.25 miles from a supermarket.

Sample size calculations for corner stores were based on the analysis of a simple difference in change in the mean of Healthy Food Availability Index (HFAI) scores. We used preliminary impact data from our previous trial (BHCK), with a reported mean change in HFAI  $\mu(\sigma) = 1.67(5.35)$  and  $\mu(\sigma) = 5.65(4.95)$  in the control and intervention groups, respectively. Due to the price incentive features (subsidy, group purchasing discounts) that will be available to BUD stores owners to stock healthier foods and beverages in phases 1 and 2, we estimate that the effect of the BUD intervention will be higher than our previous studies with corner stores. Therefore, we estimated a total sample size of 34 stores (17 per arm) for two-sample comparison of mean assuming a difference in healthy food availability (HFAI) of 6 points, variance of 24, intraclass correlation of 0.0001, type I error of 5% and power level set at 80%. We will increase our store sample size by 2 per treatment arm (n=38) to account for possible loss to follow-up. As mentioned, we will also control for baseline covariance, which will help to increase the power of the study. Some of the potential factors to control for will include store size and baseline HFAI.

The consumer sample size of this feasibility trial is intended to obtain an estimate of effect size and the variance in food consumption, purchasing, and body mass index, in order to plan a larger clinical trial, and to provide evidence of recruitment and retention ability. Therefore, the R34 pilot study is not powered to provide impact at the consumer level (which will be the primary outcomes for the full-scale clinical trial). Consumer eligibility criteria are as follows: 1) frequent consumer of the food store (shop at least once a week); 2) live/work within 1/4 mile radius from the store; 3) >21 years old and < 75 years old; 4) live in a household of at least 2 persons. We will use systematic sampling to recruit the consumer study evaluation sample in and around each of the 38 small food stores (5 adult consumers per food store).

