## Statistical Design Plan

The data analysis plan is a series of steps including data entry, data cleaning, exploratory data analysis, and multivariate analysis, led by our biostatistician ([name]) and by our economist ([name]) for the economic analysis. Data will be managed at JHU and the data manager will review data for quality. Qualitative data will be de-identified, transcribed and translated (if needed) by research assistants, kept on password protected computers, and analyzed using Atlas-ti 8.4. Quantitative data will be de-identified, entered into Microsoft Access databases and analyzed using Stata 14. These data will be collected through direct observation (e.g., availability), electronic point of sale data collection (e.g., sales), surveys (e.g., consumer purchasing), and anthropometry (e.g., BMI). We will look at the change in availability, sales, and purchasing of healthier foods scores from baseline to post-intervention comparing intervention and comparison groups, at the store and consumer levels. Models will control for covariates that predict the outcomes (e.g., store size or consumer age and sex), and standard errors will account for the clustering of repeated measures within stores.

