### Analysis of pilot trial store impact data (Aim 3)

We hypothesize that there will be significantly increased availability (stocking) and sales of healthy promoted foods (whole grain, fruit, vegetable, and low-fat, low-sugar foods) and beverages in intervention stores using the BUD app, as compared to comparison stores. Using direct observation-based stocking data, a healthy food availability index (HFAI) will be calculated, and we will initially examine the difference from pre- to

postintervention comparing intervention and control stores. We will also look at change in availability and sales of specific promoted product categories from pre- to post-intervention at each specific phase of intervention. Mixed-effect models, treating the stores as a random effect, will be used to evaluate the effect of the intervention on availability/sales of healthful food and beverage scores comparing corner store intervention and comparison groups, adjusting for covariates, such as store size and food stocking at baseline. We hypothesize that prices of some promoted foods and beverages will decrease given promoted foods/beverages will be subsidized during the first two phases of the intervention, as compared to baseline (if stocked at baseline). Furthermore, we will conduct additional tests to see if a pass-through price effect occurred related to the initial subsidy. Since the subsidy is short term (just phases 1 and 2 of the intervention), relatively small, and intended to generate initial usage of the app, we do not anticipate a significant price effect.

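### Time in business is used to stratify the stores but is not named in the Aim 3 model; committing to it in advance is a free, small improvement

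*Combined protocol and SAP*

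**What the plan says.** The design is set out under Power Calculation and Study Design. Before randomisation, stores are stratified on two factors described there as potential confounders. The first is "length of time in business at this location (>2 years vs <2 years"); the second is store size, in classes of 0 to 2 and 2 to 4 aisles. The plan is to stratify "and then randomize matched pairs to treatment versus comparison".

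Store-level covariates for the analysis appear in four places:

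- Opening of the Statistical Design Plan: "Models will control for covariates that predict the outcomes (e.g., store size or consumer age and sex"). Store size is named.
- Aim 3: "Mixed-effect models, treating the stores as a random effect, will be used to evaluate the effect of the intervention", "adjusting for covariates, such as store size and food stocking at baseline". Store size and baseline stocking are named.
- Power section, after the randomisation text: "We will control for baseline covariates of all participating stores that may predict study outcomes". No factor is named.
- Power section, after the sample size: "Some of the potential factors to control for will include store size and baseline HFAI". Store size and baseline HFAI are named.

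Time in business is named in none of the four, and no passage says that the stratification factors or the pairs will be carried into the model. The sample size is "based on the analysis of a simple difference in change in the mean of Healthy Food Availability Index (HFAI) scores".

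**The concern.** When allocation is balanced on a factor that predicts the outcome, the design removes that factor's contribution from the difference between arms. If the model omits the factor, its variance stays in the residual. The estimated standard error then exceeds the true one, the test rejects less than 5% of the time under the null, and part of the gain from stratifying is lost.

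One of the two design factors (size) is named for adjustment and the other is not. The power section also says that covariate control is meant to raise power, so naming only one factor carries out that aim only in part. What is at stake is efficiency.

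A separate and smaller matter is that a 2-aisle store fits both size classes, so its stratum and its covariate value are undefined.

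**Working it through.** **Inputs from the documents.** 19 stores per arm, randomised in pairs. Previous-trial change in HFAI: 1.67 (SD 5.35) in control and 5.65 (SD 4.95) in intervention. The difference is 5.65 − 1.67 = 3.98 and the pooled variance is (5.35² + 4.95²)/2 = 26.56. Design values: difference 6, variance 24, 80% power, 5% type I error (taken as two-sided).

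**Assumptions not in the documents.** Pairs are formed only on the two named factors. Size class splits 50/50 and explains 10% of the variance. 25% of stores are newer (10% and 50% as alternatives). The gap in HFAI change between newer and older stores runs from 0 to 4 points.

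**The plan's own figure.** The usual formula gives 2 × 24 × (1.96 + 0.84)²/6² = 10.5, so 11 stores per arm (12 by t-test), not the stated 17. With the stated inputs, 17 per arm has about 93% power and 19 about 96%. That mismatch is a separate matter and errs on the large side. Here it matters only because it leaves ample margin at 6 points.

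**Analytic check.** With newer share q = 0.25, a gap g contributes variance g² × 0.25 × 0.75 = 0.1875 g². After size, the residual variance is 0.9 × 26.56 = 23.90.

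- g = 2: 0.75, which is 2.8% of 26.56 and 3.1% of 23.90. True level ≈ 2 × [1 − Φ(1.96/√(1 − 0.031))] ≈ 4.6%.
- g = 4: 3.00, which is 11.3% of 26.56 and 12.6% of 23.90. True level ≈ 2 × [1 − Φ(1.96/√(1 − 0.126))] ≈ 3.6%.
- Standard error at g = 4: √(2 × 23.90/19) = 1.59 without the factor and √(2 × 20.90/19) = 1.48 with it. Simulated means are 1.57 and 1.47.

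**Simulation.** 19 pairs sharing both classes, treatment randomised within pair, linear model on the pre-to-post change with size, with and without time in business; 40,000 trials per setting; power at 3.98 points.

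| Gap | R² of factor | Type I without | Type I with | Power without | Power with |
|---|---|---|---|---|---|
| 0 | 0% | 5.15% | 5.14% | 68.3% | 68.2% |
| 1 | 0.7% | 4.69% | 4.78% | 68.5% | 68.8% |
| 2 | 2.8% | 4.52% | 4.82% | 68.5% | 69.5% |
| 3 | 6.4% | 4.16% | 4.94% | 69.0% | 71.4% |
| 4 | 11.3% | 3.74% | 5.04% | 69.8% | 74.1% |

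The simulation standard error of a 5% rate is √(0.05 × 0.95/40,000) = 0.11 points, so the two type I columns must be read against each other and not against 5%. The tabled run is slightly low in both columns at gaps 1 and 2. Repeats at gap 2 gave about 4.6–4.9% without and 5.0–5.2% with. Another repeat moved power from 68.3, 69.0 and 69.5% to 68.2, 69.9 and 74.0% at gaps 0, 2 and 4.

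**Sensitivity.**

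- 10% newer stores: 68.3 to 68.7% at gap 2; 69.0 to 71.0% at gap 4. 50% newer: 69.0 to 70.3%; 70.2 to 76.2%.
- Baseline HFAI also in the model (assumed R² 0.2), gaps 0, 2, 4: 77.6, 78.1, 79.5% to 77.6, 79.2, 84.3%.
- Two stores lost per arm, gaps 0, 2, 4: 63.3, 62.9, 64.2% to 63.0, 63.8, 68.6%.
- Design values (6 points, variance 24), gaps 0, 2, 4: 97.2, 97.3, 98.0% to 97.2, 97.5, 98.6%.

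**How large a gap is plausible.** With 25% newer stores, the gap implied by a given R² is √(R² × 26.56/0.1875). R² of 0.10 needs 3.8 points and R² of 0.20 needs 5.3. The first is close to, and the second above, the previous trial's whole effect of 3.98. With 50% newer stores (divisor 0.25) the gaps are 3.3 and 4.6.

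**Model form.** In 59 simulated data sets at gap 4, with pre and post scores modelled jointly and a store random intercept, the mean standard error of the group-by-period term was 1.667 with size as a main effect and still 1.667 with time in business added as a main effect. It fell to 1.574 with size by period, and to 1.465 with both factors by period.

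**The case against.** The strongest reply is that the plan already covers this. The power section calls both factors potential confounders and, in the next paragraph, promises to control for baseline store covariates that may predict outcomes. The lists in Aim 3 and the power section are illustrative. A careful analyst would include time in business, and adding it only when it proved significant recovered nearly all of the power gain in simulation. This stands in large part: the factor is unnamed, not excluded, and a reader who infers that the plan leaves it out goes further than the text. What remains is that an open list is not a commitment. The opening of the Statistical Design Plan, which controls for covariates that predict the outcomes, can be read as choosing them after seeing the data.

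A second reply is that the loss is small, conservative in direction, and rests on assumed gaps, in a feasibility pilot meant to inform a later trial. That also stands, and it sets the rating. The headline simulation is also simpler than the planned analysis: it uses the pre-to-post change, not all five stocking observations, and puts baseline HFAI in only as a sensitivity run.

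Stronger readings are tempting but unsupported. Ignoring the stratification here does not inflate type I error or bias the estimate; the error runs the other way. The documents do not show that pairs are matched on anything finer than the two factors, so they do not establish that a pair term is needed. The 2-aisle overlap does not bias the comparison, because stores are classified before randomisation. As printed, a store open exactly 2 years fits neither time class, and the upper size class reaches 4 aisles while eligibility stops below 4. Both may be equals signs lost in text conversion, and neither should be pressed.

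**Conclusion.** The point holds as a minor one. A factor used to balance the randomisation is not committed to the Aim 3 model. The consequence depends on an effect that the documents do not give. If time in business predicts nothing, nothing is lost. At a 2-point gap the cost is about 0.3 percentage points of type I error and 1 point of power at a 3.98-point effect; at a 4-point gap it is about 1.3 and 4.5 points. Gains of the latter size need a gap about as large as the previous trial's whole treatment effect, so the real gain is probably small. Power at 6 points stays far above 80% with or without the factor.

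The direction is certain if the factor is prognostic. The sizes rest on the assumed 25% share of newer stores, the assumed R² for size, and pairing on the two factors only. The overlap at 2 aisles is clerical.

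**What to change.** In the Aim 3 model, pre-specify time-in-business class, size class and baseline HFAI as fixed effects, whatever their observed association with the outcome. Fit them in a model for the change, or for the follow-up score given baseline. If pre and post scores are modelled jointly with a store random intercept, interact the two stratification factors with period, because main effects alone leave the treatment standard error unchanged. No pair term is needed if pairs are formed only on these two factors; if they are matched more finely, say so and include the pair.

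The cost is one sentence and one degree of freedom: power goes from 68.3% to 68.2% if the factor predicts nothing, or from 63.3% to 63.0% after losing two stores per arm.

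As an accompanying clerical edit, assign 2-aisle stores to one size class, and check that the time classes cover exactly 2 years and that the upper size class agrees with the eligibility limit.

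### The Aim 3 model names neither the matched pair nor time in business, both used to randomise stores, so some precision on HFAI may be lost (minor)

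*Combined protocol and SAP*

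**What the plan says.** Under Power Calculation and Study Design, individual stores are the unit of randomisation. They are first stratified by two binary factors, time in business at the location and store size in aisles. The plan goes on: "and then randomize matched pairs to treatment versus comparison". With 19 stores per arm this implies 19 pairs, each with one store in each arm.

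The same section sizes the trial without the pairs: "we estimated a total sample size of 34 stores (17 per arm) for two-sample comparison of mean". It assumes a difference of 6 HFAI points and a variance of 24, and adds two stores per arm for loss to follow-up.

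For the analysis, the Aim 3 section states: "Mixed-effect models, treating the stores as a random effect, will be used to evaluate the effect of the intervention". Its covariates are given as examples, namely store size and baseline stocking. The power section promises control for baseline covariates that may predict outcomes and again names store size and baseline HFAI. The opening of the Statistical Design Plan adds that "standard errors will account for the clustering of repeated measures within stores". Nowhere is a pair or stratum term named, and time in business is never listed as a covariate.

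**The concern.** The pair is the randomisation block, and its two members always go to opposite arms. If they tend to change alike, the difference between arms varies less than it would between independent groups. A store random effect cannot capture this, because each store belongs to one arm and the similarity lies between stores. Nor can standard errors that allow only for repeated measures within a store.

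Covariates can capture it, but only for the factors that are entered. Store size is one of the two stated factors and is named. Time in business is the other and is not. The plan also does not say whether pairs within a stratum are matched on anything more. What the covariates miss inflates the standard error of the HFAI contrast, and in the same way that of store sales. The section on using the data to power the main trial says the pilot is meant to give adequate precision, so avoidable loss of precision matters here.

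**Working it through.** **Inputs.** From Power Calculation and Study Design: difference 6, variance 24 (SD 4.90), type I error 5% (taken as two-sided; the plan does not say), power 80%, 17 stores per arm before the allowance for loss. Assumed, because the documents do not give it: the within-pair correlation ρ of HFAI change.

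**1. The plan's own figure.** Stores per arm = 2σ²(z₀.₉₇₅ + z₀.₈₀)²/Δ² = 2 × 24 × (1.960 + 0.842)²/36 = 10.5, so 11, or 12 with the exact t. The stated 17 does not follow from the stated inputs, and an intraclass correlation of 0.0001 does not change that. This mismatch is a separate matter. What counts here is that 17 per arm has about 93% power (t-test) for 6 points.

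**2. Effect of ignoring pairs.** The true variance of the arm difference is 2σ²(1 − ρ)/n; an independent-arms analysis reports 2σ²/n. At n = 17 and ρ = 0.2 the true standard error is √(2 × 19.2/17) = 1.50, against √(48/17) = 1.68 reported.

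**3. What the covariates recover.** Simulation with 17 pairs and total variance 24, where paired stores share only the two stated factors and each factor takes either value with equal probability. A factor with effect b then contributes b²/4 to the variance: b = 4.38 gives 4.80, so ρ = 4.80/24 = 0.20; two factors with b = 4 give 8/24 = 0.33. Cells show mean 95% half-width and type I error.

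| Source of similarity | ρ | Store size only | Both factors | Fixed pair term |
|---|---|---|---|---|
| Store size | 0.20 | 3.04, 4.9% | 3.04, 4.9% | 3.14, 4.8% |
| Time in business | 0.20 | 3.39, 2.9% | 3.05, 4.8% | 3.14, 4.8% |
| Equal parts | 0.33 | 3.10, 3.0% | 2.78, 5.3% | 2.87, 5.0% |

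Closed-form check of the second row, both factors: t(30 df) × 1.503 = 2.042 × 1.503 = 3.07. The loss in that row is 3.39/3.05 = 1.11, an interval about 11% wider. Baseline HFAI is not in the simulation, so ρ should be read as what remains after adjusting for it.

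**4. Power at 6 points, second row.** By normal approximation: (6 − 3.39)/1.503 = 1.74, about 96%, against (6 − 3.05)/1.503 = 1.96, about 97.5%. With no similarity it is about 93%, as in step 1.

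**5. Range for ρ.** Unadjusted two-sample test against a strictly paired test, 17 pairs:

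| ρ | Type I error, unpaired | Half-width, unpaired | Half-width, paired |
|---|---|---|---|
| 0 | 5.0% | 3.42 | 3.56 |
| 0.1 | 3.9% | 3.42 | 3.38 |
| 0.2 | 3.0% | 3.42 | 3.19 |
| 0.3 | 2.2% | 3.42 | 2.98 |
| 0.5 | 0.8% | 3.42 | 2.52 |

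The paired interval is the narrower one only above ρ = 1 − (2.037/2.120)² = 0.077 (0.068 with 19 pairs).

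**6. A random pair effect at this size.** One change score per store, no covariates, 17 pairs, REML with the pair variance bounded at zero. Type I error with normal-based inference is 7.7%, 7.2%, 7.0% and 6.9% at ρ = 0, 0.1, 0.2 and 0.5. With a t reference (16 df if the pair variance is positive, otherwise 32) it is 6.1%, 5.6%, 5.3% and 5.1%. The pair variance is estimated as zero in 50%, 35% and 21% of trials at ρ = 0, 0.1 and 0.2.

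**The case against.** The strongest reply is that covariate adjustment already does the work. That is right for store size: the first row of the step 3 table shows no loss. The covariate lists are also open-ended, so time in business could still be entered. But nothing commits the analysis to it, and the second and third rows show what its omission can cost.

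It can also be said that ρ is undocumented, may be near zero after adjusting for store size and baseline HFAI, and that a strictly paired analysis would then do worse. This stands. So does the point that the error is in the conservative direction, in a feasibility pilot. The plan's intraclass correlation of 0.0001 does not settle the matter, since the unit it refers to is not stated.

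A reader might infer that all similarity within pairs is left in the error and that the HFAI interval is therefore certainly too wide. The documents do not support this, because one of the two stated factors is already a named covariate and no correlation is given. The figures at ρ = 0.5 would need that much correlation to remain after adjustment, for which the plan offers no evidence.

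**Conclusion.** The point holds in a limited form. The randomisation uses time in business and matched pairs, and the Aim 3 model names neither. If paired stores are alike in ways that store size and baseline HFAI do not capture, precision is lost and the test is conservative. Under the assumed ρ of 0.2 due wholly to time in business, the half-width is 3.39 instead of 3.05 points, with type I error near 3% instead of 5%. With similarity from store size only, or none, there is no loss.

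A reader might also conclude that the trial is too small or its test invalid. Neither follows. The two-sample calculation is conservative if paired stores change alike, the omission causes no bias and no excess of false positives, and power for 6 points is above 93% whether or not the second factor is entered. Severity is minor.

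**What to change.** In the Aim 3 analysis section, enter both stratification factors, time in business and store size, as fixed covariates alongside baseline HFAI in the models for HFAI and sales. State how pairs are formed within strata.

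Only if pairs are matched on something beyond these two factors, also add a random intercept for pair, with store nested within pair. This keeps a store whose partner is lost. Specify small-sample t-based inference, for example Kenward-Roger, because normal-based inference gives about 7% type I error with 17 pairs (step 6).

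In Power Calculation and Study Design, note that the two-sample calculation ignores the pairing and is conservative if paired stores change alike.

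**Cost.** No new data or stores are needed. The added factor uses one degree of freedom. A pair term costs up to about 1.5 to 2.5 points of power if the residual correlation is zero and a strictly paired test is used: from 93% to 92% at 6 points, and from 80% to 77% at 4.85 points, the difference for which 17 per arm gives 80% power at variance 24.

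### The 17 stores per arm at 80% power do not follow from the printed inputs: an independent-stores t-test needs 12 per arm, and 17 per arm has about 93% power

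*Combined protocol and SAP*

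**What the plan says.** All of this is in the Statistical Design Plan, under Power Calculation and Study Design.

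- The calculation: "Sample size calculations for corner stores were based on the analysis of a simple difference in change in the mean of Healthy Food Availability Index".
- The result: "we estimated a total sample size of 34 stores (17 per arm) for two-sample comparison of mean".
- The inputs: a difference of "6 points, variance of 24, intraclass correlation of 0.0001, type I error of 5% and power level set at 80" per cent.
- The attrition allowance comes afterwards: "We will increase our store sample size by 2 per treatment arm (n=38) to account for possible loss to follow-up".
- The design: "This is a randomized group-treatment trial, where individual stores will be randomized to two study conditions". After stratifying on time in business and store size, the plan will "then randomize matched pairs to treatment versus comparison".

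The section also says that clustering may arise because intervention owners share the app and may interact through it. It gives no number of groups, group size, degrees of freedom or sidedness, and names no formula or software. The previous trial's changes in HFAI are given as mean 1.67 (SD 5.35) in control stores and 5.65 (SD 4.95) in intervention stores.

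**The concern.** The sentence contains everything an ordinary two-sample calculation needs except sidedness, so the reader should be able to recover 17 per arm. The ordinary calculation gives 12. A gap of 5 stores per arm, or 10 in total, is too large for rounding or for the choice between the normal and t formulas.

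This is the plan's only power statement, and both the 34 and the 38 stores rest on it. As printed, a reader cannot tell which test, or which difference, the trial was sized for. The possible explanations also differ in consequence: some leave ample spare power and one leaves almost none. The plan intends to use this pilot's data to revise the sample size of the main trial, so the method should be one that can be repeated.

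**Working it through.** **Inputs.** From Power Calculation and Study Design: difference d = 6, variance s² = 24 (SD 4.899), intraclass correlation 0.0001, type I error 5%, power 80%, equal arms. Sidedness is not stated, so two-sided is assumed first.

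**Attempt to reproduce 17 per arm**

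1. Normal formula: n = 2(1.960 + 0.842)² × 24 / 6² = 10.47, so 11 per arm.
2. Two-sample t-test, noncentral t with 2n − 2 degrees of freedom and noncentrality 6/√(2 × 24/n):

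| Stores per arm | Power for 6 points | Difference detectable at 80% |
|---|---|---|
| 11 | 78.0% | – |
| 12 | 81.8% | – |
| 17 | 93.3% | 4.85 |
| 19 | 95.7% | 4.58 |

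The requirement is therefore 12 per arm, and the stated 17 is not reproduced.

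**Explanations that keep the printed inputs**

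- *Intraclass correlation as a design effect.* 1 + (m − 1) × 0.0001 is 1.0016 for m = 17 and 1.0033 for all 34 stores in one cluster. The required n is essentially unchanged.
- *One-sided test.* 10 per arm, which is further from 17.
- *Matched pairs analysed as pairs.* Assuming no within-pair correlation, the variance of a pair difference is 48 and there are n − 1 degrees of freedom. Twelve pairs give 78.0%, 13 give 81.7% and 17 give 91.8%. The requirement is 13.
- *Loss to follow-up.* The allowance of 2 per arm takes 17 to 19, so it is not part of the 17.

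**Changes that do give 17 per arm**

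- Difference 5 with variance 24: 17 per arm, 82.3% power.
- Difference 6 with variance 36: 17 per arm, 80.7% power.
- All printed inputs kept, but the test referred to a t distribution with few group-level degrees of freedom. These are an assumption, since none are printed:

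| Degrees of freedom | Stores per arm for 80% | Power with 17 per arm |
|---|---|---|
| 3 | 25 | 67% |
| 4 | 19 | 76% |
| 5 | 17 | 81% |
| 6 | 16 | 84% |
| 10 | 13 | 89% |
| 15 to 32 | 12 | 92% to 93% |

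**Sensitivity to the variance.** The previous trial's SDs give variances of 4.95² = 24.50 and 5.35² = 28.62. Their simple average is 26.56, which assumes equal arms because the arm sizes are not given. With independent stores and a two-sided t-test:

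| Variance | 17 per arm: power for 6 | 17 per arm: detectable | 19 per arm: power for 6 | 19 per arm: detectable |
|---|---|---|---|---|
| 24.50 | 92.9% | 4.91 | 95.3% | 4.62 |
| 26.56 | 90.8% | 5.11 | 93.7% | 4.81 |
| 28.62 | 88.7% | 5.30 | 92.0% | 5.00 |

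**The case against.** The best defence is that the benchmark of 12 treats stores as independent, whereas the plan describes a group-treatment trial, expects clustering through the app, and lists an intraclass correlation. A group-based test with 5 degrees of freedom gives exactly 17 (81.2%) with every printed number intact. On that view nothing printed is wrong and the plan is only under-reported. This is possible, but it needs a figure that appears nowhere in the plan, and the result is sensitive to it: 4 degrees of freedom would need 19 per arm and 6 would need 16. It explains how 17 might have arisen. It does not make the statement reproducible.

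Two parts of the objection stand. First, the reassurance about enrolment depends on stores being independent; with 4 group-level degrees of freedom, 17 evaluable stores per arm have 76% power. Second, 93% is power for the assumed 6 points, not for the previous trial's difference of 5.65 − 1.67 = 3.98. For that difference, 17 per arm has about 59% power at variance 26.56 and 63% at variance 24. The plan gives its reason for expecting a larger effect, so that is a separate matter, but restated power should not be read as covering it.

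It can also be said that a feasibility pilot needs less precision in its power statement. However, the plan says that it is powered at store level and hypothesises a significant store-level effect under Aim 3, so the statement should be checkable.

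**Conclusion.** The concern holds. On the printed inputs, with independent stores and a two-sided 5% t-test, the requirement is 12 per arm rather than 17, and 17 per arm has 93.3% power rather than 80%. No calculation tried that uses only the printed inputs gives 17. Either the difference or variance printed is not the one used, or a group-based method was used and its degrees of freedom were left out. The documents do not show which.

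This does not show an underpowered trial. With independent stores the discrepancy is conservative, and it remains so across the previous trial's variances (88.7% to 92.9% for 6 points with 17 per arm). That conclusion would not survive a test with very few group-level degrees of freedom, which is why the missing input matters.

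**What to change.** Correct the power paragraph and keep 38 stores. State the test and its sidedness, then do whichever of the following applies:

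- If another difference or variance was used, print it.
- If a group-based method was used, print the number of groups and the degrees of freedom, with the resulting power.
- If neither applies, replace the claim with wording such as: Treating stores as independent (two-sided 5%), 17 evaluable stores per arm give about 93% power for a 6-point difference in HFAI change and 80% power for about 4.85 points at variance 24. Across the previous trial's variances (24.5 to 28.6; simple average 26.6, assuming equal arms), power for 6 points is about 93% to 89%, and the difference detectable at 80% power is 4.9 to 5.3 points.

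The cost is a wording change to one paragraph, with no change to enrolment on the independent-stores reading. If the missing input proves to be 4 or fewer group-level degrees of freedom, 17 evaluable stores per arm fall short of 80%, and the paragraph should say so.
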